Patients with rotated lower incisors (more than 30 degree) are treated with circumferential supracrestal fiberotomy 2 weeks prior to retention.

Group A: Retention with a CTC in the mandible and Essix retainer in the maxilla.

Two weeks before debonding an impression of the mandibular jaw is taken in order to manufacture the CTC retainer. The CTC-retainer is bonded to the canines directly after debonding. The Essix retainer is manufactured on dental casts after debonding and handed out to the patients the same day. The patients are instructed to wear the Essix retainer full-time the first week and thereafter night only.

Group B: Retention with Essix retainers in the maxilla and mandible.

The Essix retainers are manufactured on dental casts after debonding and handed out to the patients the same day. The patients are instructed to wear the Essix retainers full-time the first week and thereafter night only.

Dental cast are obtained at the debond appointment (T1) and at the follow-up controls after six months (T2), 18 months (T3) and 5 years (T4) for both groups. All measurements on casts are made with an electronic digital calliper to the nearest 0.25 mm. Comparisons within and between groups are performed.

Stability after retention is also analyzed depending on diagnoses before treatment and treatment outcome.

Outcome measures on the dental casts are as follow:

- Little's irregularity index
- Intercanine width
- Intermolar width
- Arch length
- Overjet
- Overbite

To assess measurement precision and reliability, 30 randomly selected dental casts are measured by the same examiner at a five weeks interval.

At the visit two weeks in retention and at the follow-up visits after 6, 18 and 60 months the patients assessed questionnaires in order to evaluate their experience of retention with an Essix retainer and a CTC respectively. The questionnaires include self-report questions from a previous study where reliability and face validity were found to be acceptable (Feldmann et al 2007). In addition, a few questions modified for this study are included. The fit of the retainers and the CTC are checked at each visit. All questionnaires are evaluated and compared between the two groups

Statistical analysis

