Descriptive statistics are calculated for both groups (median, interquartile ranges, and test for normal distribution). The post-treatment changes are described by comparing measurements at debond (T1), after 6 months (T2), after 18 months (T3), and after 5 years (T4). Generalized estimating equations (GEE) are used to estimate the effect of the two treatment groups over time for the outcome variables. In the GEE analysis, all digital measurements, extraction therapy, sex, retention group, and time and the interaction of time with retention group are tested as explanatory variables (predictors). The GEE correlation structure is set to autoregressive, a convenient option for models with time-dependent observations.

Mann-Whitney U tests are used to analyse and compare the answers on questionnaires for the VFR/VFR and VFR/CTC group. Spearman's correlation coefficient is calculated to determine the relationship between patients' perceptions, self-reported VFR compliance, and LII. Demographic data are analysed with cross tabulations. P-values less than 0.05 are considered statistically significant.

Ethical considerations

All patients and parents are given oral and written information and sign a written consent before being included in the trial. The participation is voluntary and patients can leave the trial at any time without giving reasons.

Both of the tested retention-appliances are common and used frequently in orthodontic practices. The impressions at the follow-up visits are additional for this study.

The Ethics Committee of Uppsala (Regionala etikprövningsnämnden) approved the study protocol (diarienummer: 2009/177).

Research projects:

1. Effectiveness of Essix retainer versus bonded CTC in the mandibular arch after 6 and 18 months.

Aim: The aim of this project is to evaluate and compare stability in the mandibular arch 6 and 18 months after retention with an Essix retainer compared to retention with a bonded cuspid-to-cuspid retainer (CTC).

Material and methods: 104 patient are randomized into 2 groups; CTC (group A) and Essix retainer (group B). Little's Irregularity Index, intercanine width, intermolar width, arch length, overjet and overbite are measured on dental casts and analysed at the debond appointment, after 6 months and after 18 months.

The null hypothesis is that there is no difference in retention capacity between Essix retainer and cuspid-to-cuspid retainer.

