The results from this study will be presented at the Swedish Dental Congress in 2018.

2. Evaluation of patients' perception of the retention appliances by questionnaires after 6 months and 18 months.

Aim: The aim of this project is to evaluate and compare patients' perception of their retention with an Essix retainer compared to retention with a bonded cuspid-to-cuspid retainer (CTC) 6 and 18 months after debonding.

Material and methods: 104 patients assessed a questionnaire after debonding and at the follow-up visit after six and 18 months to evaluate their experience of retention with an Essix retainer and a CTC respectively.

The null hypothesis is that there is no difference in patients' perception between Essix retainer and cuspid-to-cuspid retainer.

The results from this study will be presented at the Swedish Dental Congress in 2019.

3. Long-term stability in the mandibular arch after 5 years of retention.

Aim: The aim of this project is to evaluate and compare stability in the mandibular arch 5 years after retention with an Essix retainer compared to retention with a bonded cuspid-to-cuspid retainer (CTC).

Material and methods: 104 patients are randomized into 2 groups; CTC (group A) and Essix retainer (group B). Little's Irregularity Index, intercanine width, intermolar width, arch length, overjet and overbite are measured on dental casts and analysed after 5 years of retention.

The null hypothesis is that there is no difference in retention capacity between Essix retainer and cuspid-to-cuspid retainer.

The results from this study will be presented at the Swedish Dental Congress and the European Orthodontic Society Congress in 2021.

4. Retention stability in the maxilla depending on the diagnoses before treatment and on the treatment outcome after fixed orthodontic appliances.

Aim: The aim of this project is to evaluate and compare stability in the maxilla 6 months, 18 months and 5 years after retention with an Essix retainer.

Material and methods: Dental casts of 104 patients are measured and analyzed concerning overbite, overjet, intercanine width, intermolar width and arch length after 6 months, 18 months and 5 years of retention.

The null hypothesis is that there is no difference in retention capacity for Essix retainer in the maxilla concerning diagnosis before treatment, treatment outcomes, treatment time and age at start of treatment.

Relevance

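### Project 2 tests one null on patient perception with several unadjusted 0.05-level tests and no rule for rejecting it, so its error rate is not held at 5%

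*Combined protocol and SAP*

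**What the plan says.** Under Research projects, project 2 has its own aim and one null: "The null hypothesis is that there is no difference in patients' perception between Essix retainer and cuspid-to-cuspid retainer". Its title and aim name 6 and 18 months. Its methods add an earlier questionnaire: "104 patients assessed a questionnaire after debonding and at the follow-up visit after six and 18 months".

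Materials and methods describes the instrument as self-report questions taken from a previous study, and continues: "In addition, a few questions modified for this study are included". So there is more than one question, but the number is not given. The same section lists the trial-wide schedule ("At the visit two weeks in retention and at the follow-up visits after 6, 18 and 60 months the patients assessed questionnaires") and ends: "All questionnaires are evaluated and compared between the two groups".

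The Statistical analysis section gives the method, "Mann-Whitney U tests are used to analyse and compare the answers on questionnaires for the VFR/VFR and VFR/CTC group", and the only decision threshold, "P-values less than 0.05 are considered statistically significant". It names no summary score, global test or repeated-measures model for the questionnaires. No section names a primary item or visit, a hierarchy or an adjustment, or labels the perception analysis exploratory.

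**The concern.** One null is put to several tests, each with its own 5% chance of a false positive, and the plan does not say how their results combine into a decision. Nothing prevents the null from being rejected because one question at one visit falls below 0.05, even if that question was singled out after the data were seen. A claimed difference in perception could then be a chance finding.

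Perception is not incidental here. It is in the trial title and the Aim, it has a project of its own, and the Relevance section calls it an important factor on which little is known.

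**Working it through.** The plan gives no family-wise error rate, so there is no figure of its own to reproduce.

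**Inputs from the document**
- Level per test: 0.05 (Statistical analysis). Sidedness is not stated; two-sided is assumed.
- Visits in project 2: 2 by its aim (6 and 18 months), 3 by its methods (also after debonding).
- Items: more than one (Materials and methods); number not given.
- Group size: 52 per arm, 104 in total.

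**Assumptions**
- Each item is tested at each visit, so the number of tests is K = items × visits.
- Any one P < 0.05 counts against the null.
- The correlation between test statistics is the same for all pairs and lies between 0 and 0.7.
- Item counts of 2, 5 and 10 are used to show the range. One item is included as a case below what the text describes.

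**Formulas**
- Independent tests: FWER = 1 − 0.95^K.
- Common correlation r: FWER = 1 − ∫ φ(u) [Φ((c − √r·u)/√(1−r)) − Φ((−c − √r·u)/√(1−r))]^K du, with c = 1.96, by numerical integration.

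**Results**

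| Items × visits | K | r = 0 | r = 0.7 |
|---|---|---|---|
| 1 × 2 | 2 | 1 − 0.95² = 9.75% | 8% |
| 1 × 3 | 3 | 1 − 0.95³ = 14.3% | 10.9% |
| 2 × 2 | 4 | 1 − 0.95⁴ = 18.5% | 13% |
| 5 × 3 | 15 | 1 − 0.95¹⁵ = 53.7% | 26% |
| 10 × 3 | 30 | 1 − 0.95³⁰ = 78.5% | 34% |

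Two items at two visits is the smallest count that fits the text.

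**Check with the planned test.** Tie-corrected Mann-Whitney tests were simulated with 52 per arm and five-category answers. The correlation was 0.5 between items and 0.5 between visits, so pairs that differ in both are less correlated. A single test kept about 5%. Five items at three visits gave 44% and ten items at three visits 62%, both inside the ranges above.

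**Effect of adjustment.** Holm's first step compares the smallest P-value with 0.05/K: 0.05/4 = 0.0125, 0.05/15 = 0.0033, 0.05/30 = 0.0017. When no item differs, the chance of any false rejection is the same as under Bonferroni. In the same simulation it was 3.9% for 5 × 3 and 3.6% for 10 × 3.

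The 60-month questionnaire lies outside project 2 and is not counted. Nor are the Spearman correlations, whose number is not given.

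**The case against.** The strongest reply is that two steps of the argument are inferred. The plan does not say in so many words that every item is tested at every visit. The earlier instrument might yield domain scores, and the document does not describe its scoring. Nor does the plan say that one significant item rejects the null. The null could be read as a general heading, with each question reported on its own terms, and then the per-item error rate is what matters. A consistent pattern across items and visits would also be informative without any adjustment.

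These points stand as limits on what can be claimed. A reader might infer that the plan commits to rejecting on any single item, or that the true error is 54% or 79%. The document supports neither. It gives no rejection rule at all, and the larger figures rest on assumed item counts and, at their upper ends, on independence, which is unlikely for answers from the same patients at repeated visits.

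The Aim puts stability first and says perceptions are also evaluated, which suggests a secondary role. But a secondary role does not make the analysis exploratory, and project 2 states a formal null.

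The reply does not remove the gap. The plan refers to tests in the plural, on the answers to more than one question, and a Mann-Whitney test does not pool visits. Even if the questionnaire were reduced to one score, testing it at two visits would give 8% to 9.75%.

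**Conclusion.** The concern holds in this form: as written, the plan does not hold the error for project 2's single null at 5%, because several tests at 0.05 bear on it and no rule says how they decide it. On the smallest reading of the text, two items at two visits, the error is 13% to 18.5%. It rises with the number of items, to 26% to 54% for five items at three visits and 34% to 79% for ten.

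These figures assume item-by-visit testing, rejection on any one significant result, two-sided tests, and a common correlation of 0 to 0.7. The direction is secure under that rejection rule. The size is not, because the item count is not given. The point affects inference in one of four projects and does not touch the stability comparison.

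**What to change.** In the Statistical analysis section, state that project 2's null is rejected only if at least one item-by-visit Mann-Whitney test is significant after Holm adjustment across all project 2 perception tests. List the items and visits that make up that set.

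Alternatively, the sponsor may prespecify, before analysis, one perception item and one visit of its own choice as the 0.05-level test. All other items and visits would then be reported as estimates with confidence intervals and no claim of significance. Nothing in the document favours a particular item, visit or sum score; the aim gives 6 and 18 months equal standing.

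Either option is a change of wording and needs no further patients or data. The cost of Holm is lower power for individual items: with 15 tests the smallest P-value must be at or below 0.0033. The cost of the alternative is that no significance claim can be made for any other item or visit.

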Only a few studies have analyzed patients' perception of orthodontic treatment (Bennett et al 1999, Hichens 2007, Feldmann et al 2012). Very few studies have analyzed patients' perception of retention appliances. Kumar and Bansal (2011) compared in a prospective study the effectiveness and acceptability of Essix and Begg retainers. They found that both appliances allowed some relapse but the differences were small and not clinically significant. The patients liked the comfort and appearance of the Essix retainer and preferred the Begg retainer for chewing and biting.

Although retention is a decisive factor for successful orthodontic treatment there are no evidence-based recommendations in the literature for retention appliances considering diagnoses before treatment such as vertical and skeletal deviations, the type of orthodontic movement (e.g. expansion or extraction cases) or for patients treated with fixed appliances and orthognathic surgery. Especially for patients with orthognathic surgery the choice of retention method and prevention of relapse are crucial since both skeletal and dental changes occur during treatment.

Materials and methods

The study is conducted at the Orthodontic Clinic, Gävle, Sweden and consists of 104 patients. All patients are treated with fixed appliances in the upper and lower jaw (standard .022 straight wire), both with and without extractions.

Patients treated with Rapid Maxillary Expansion (RME), orthognathic surgery, segmented appliance and patients with syndromes or agenesis of a mandibular incisor were excluded from the trial.

All patients who meet the inclusion criteria are invited to enter the trial. One experienced orthodontist (AK) provides the patients and parents with both oral and written information about the study protocol. After written consent is obtained from both the patient and parent the patients are randomized in blocks and stratified by gender into two groups. The allocation sequence is computer generated by a statistician at Gävleborg Count Hospital and concealed in opaque envelopes until randomization.

The patients are randomized into two groups with 52 patients in each group. All patients have Essix retainers in the maxilla covering all erupted teeth. The extension of the Essix retainers in the mandible covers only the dentition from first premolar to first premolar. The CTC-retainer is bonded to lingual surfaces of the mandibular canines.

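### The GEE predictor list does not limit cast measurements to debond (T1) values, so post-treatment outcomes may be adjusted for when the retainer effect is estimated

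*Combined protocol and SAP*

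**What the plan says.** The Statistical analysis section says that GEE models are "used to estimate the effect of the two treatment groups over time for the outcome variables". The next sentence gives the explanatory variables: "In the GEE analysis, all digital measurements, extraction therapy, sex, retention group, and time and the interaction of time with retention group are tested". No visit is attached to the digital measurements.

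Materials and methods shows what they are: "All measurements on casts are made with an electronic digital calliper to the nearest 0.25 mm". Casts are taken at debond (T1), 6 months (T2), 18 months (T3) and 5 years (T4). Under the line "Outcome measures on the dental casts are as follow" come Little's irregularity index (LII), intercanine width, intermolar width, arch length, overjet and overbite. Both types of retainer are fitted after debonding, on the same day, so T2 to T4 values are post-treatment.

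Under Research projects, Project 1 has these six measures "measured on dental casts and analysed at the debond appointment, after 6 months and after 18 months". Project 3 analyses them after 5 years. Both test the null hypothesis that the two retainers do not differ in retention capacity.

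**The concern.** The predictor list and the outcome list contain the same variables, and the list also carries retention group and group-by-time. Taken literally, each outcome would even predict itself, so some restriction must be intended, but none is stated. Nor does the text say which measurements enter which outcome's model, or which fit supplies the reported retainer effect.

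As worded, an analyst could follow the plan and adjust the LII comparison for intercanine width at the same follow-up visit. Width at that visit is measured after the retainers have acted. If they affect width, and width is correlated with LII, the adjusted group term is no longer the total effect of the randomised retainers. It can show an effect where none exists or shrink a real one. The central comparison in Projects 1 and 3 would then depend on a choice left to the analyst.

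**Working it through.** **No figure of the plan to reproduce.** The documents give 104 patients, 52 per group, and no SD, effect size, correlation or power. The check is therefore a reading of the text, set out above, plus an illustration of what the open choice can do.

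**Inputs.** From the documents: n = 52 per group, significance level 0.05, autoregressive working correlation. Assumed and varied: the group difference in width at follow-up in width SDs (d), the within-group correlation of width with LII (r), and a two-sided test.

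**Single visit, no true LII effect, model adjusted for concurrent width.**

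- False group effect, in LII SDs: r × d in size, with sign opposite to r × d.
- Standard error: √(1 − r²) × √(2/52 + d²/102), where 102 = 104 − 2 is the within-group degrees of freedom for width.
- Example, d = 0.5 and r = 0.5: effect 0.25; SE = 0.866 × √(0.03846 + 0.00245) = 0.175; ratio 0.25/0.175 = 1.43. Against a critical t of 1.98 on 101 degrees of freedom, this gives rejection in about 29% of trials.

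Simulation (20,000 replicates per cell, complete data, width SD 2.0 to 0.5 mm, width difference 0.50 mm) agrees with the formula:

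| Width SD (mm) | d | r = 0.1 | r = 0.3 | r = 0.5 |
|---|---|---|---|---|
| 2.0 | 0.25 | 5.3% | 6.8% | 10.9% |
| 1.5 | 0.33 | 5.3% | 8.2% | 15.8% |
| 1.0 | 0.50 | 5.6% | 11.7% | 28.8% |
| 0.5 | 1.00 | 7.2% | 29.8% | 74.1% |

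With no width difference, or r = 0, rejection is about 5%. Without the width covariate it is 4.7 to 5.5%.

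**Repeated visits.** AR(1) GEE, robust standard errors, T1 LII as covariate, assumed within-patient correlation 0.6, no width difference at T1 and a constant one afterwards, test at the last visit, 3,000 replicates per cell. Rejection at d = 0.25 / 0.50 / 1.0:

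| Analysis | r = 0.1 | r = 0.3 | r = 0.5 |
|---|---|---|---|
| Project 1 (T2 and T3) | 6 / 6 / 8% | 8 / 12 / 28% | 11 / 29 / 73% |
| Project 3 (T2 to T4) | 6 / 6 / 7% | 7 / 13 / 31% | 12 / 29 / 76% |

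With width limited to its T1 value, rejection is 4.5 to 6.2% throughout.

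**Opposite harm: a real effect hidden.** Take a true LII effect of 0.50 SD and a covariate shifted 0.5 SD in the same direction. The adjusted effect should be 0.50 − r × 0.5, which is 0.35, 0.25 and 0.15 at r = 0.3, 0.5 and 0.7. Simulation gave 0.36, 0.25 and 0.15. With T1 covariates only it gave 0.50 to 0.51.

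**The case against.** The sentence is a summary list of variables tested, not a model formula. Benign readings exist: T1 values only, predictors tested one at a time, or a list written partly for the predictor questions of Project 4. Materials and methods also says that stability is analysed by diagnosis and treatment outcome, and treatment outcome most naturally means status at debond, which favours the T1 reading. All this stands as evidence of possible intent. None of it settles the mandibular GEE. Project 4 concerns the maxilla, where every patient has the same type of retainer, so it does not explain why retention group and group-by-time are in the list.

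The illustration is also loosely tied to this trial. For the removable retainer, "The extension of the Essix retainers in the mandible covers only the dentition from first premolar to first premolar"; for the fixed one, "The CTC-retainer is bonded to lingual surfaces of the mandibular canines". Both involve the canines, so the retainers may hardly differ in intercanine width. The rates above 70% need a full 1 SD difference together with r = 0.5. At r = 0.1 and d up to 0.5, the GEE rates (6%) cannot be told apart from those of a model without width (5.4 to 6.1%). This is fair, and it limits the claim about size. It does not remove the defect, because the trial treats differences in all six measures as an open question.

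If the retainers do differ in width, a general null on retention capacity is already false, so the error concerns the conclusion about LII specifically. That qualification stands.

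Finally, the impression for the bonded retainer is taken two weeks before debonding, so allocation may precede T1. T1 still precedes both retainers, and they cannot have affected it.

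**Conclusion.** The concern holds as a statement about what the plan permits. The model that estimates the retainer effect lists the outcome measurements as predictors and does not exclude their post-treatment values. It is not shown that the analysis will be done that way, nor that bias would follow. Bias needs both a retainer effect on the added measurement and a correlation of that measurement with the outcome, and the documents give no figure for either.

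On the assumed inputs, the distortion runs from negligible (r near 0.1, or a small difference in the covariate) to serious. A middle case of d = 0.5 and r = 0.3 to 0.5 gives about 12 to 29% false rejection instead of 5%. Only one added covariate was examined, not the full set of six. The point should be fixed because it bears on the main randomised comparison and the remedy is free. Confidence is medium, since the sponsor may have meant T1 values all along.

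**What to change.** **Core change, one sentence in Statistical analysis:** in the GEE that gives the retention-group effect, no T2 to T4 cast measurement is a predictor, and any cast covariate is its T1 (debond) value.

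**Recommended with it:**

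- Name the model for each outcome. Use the follow-up visits as responses (T2 and T3 for Project 1, with T4 added for Project 3). Include retention group, time, group-by-time, the T1 value of the same outcome, extraction therapy and sex. Sex belongs there because patients are "randomized in blocks and stratified by gender into two groups".
- Keeping T1 as a response, with group-by-time as the test, is an acceptable alternative. The T1 value of that outcome is then not also a covariate.
- Put associations between concurrent cast measurements, and the Project 4 predictor questions, in separate exploratory models from which no retainer effect is reported.

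**Cost:** one to three sentences of wording. No new data, no extra patients and no change to the reporting schedule. If T1 values were always intended, the change only records that.

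### Cheap improvement: adjust the GEE for the debond (T1) value of the same outcome and fix group-by-visit in the model, rather than leaving T1 as a response and the interaction as a tested term

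*Combined protocol and SAP*

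**What the plan says.** The Statistical analysis section of the combined protocol and SAP is the only description of the model. Its purpose is stated as "Generalized estimating equations (GEE) are used to estimate the effect of the two treatment groups over time for the outcome variables". On predictors it says that "all digital measurements, extraction therapy, sex, retention group, and time and the interaction of time with retention group are tested as explanatory variables (predictors", and on the covariance that "The GEE correlation structure is set to autoregressive". No rule says what follows from testing a term.

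T1 appears only as one of the compared visits: "The post-treatment changes are described by comparing measurements at debond (T1), after 6 months (T2), after 18 months (T3), and after 5 years (T4". Under Research projects, the project 1 outcomes "are measured on dental casts and analysed at the debond appointment, after 6 months and after 18 months", and those of project 3 "are measured on dental casts and analysed after 5 years of retention".

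On timing, Materials and methods says "After written consent is obtained from both the patient and parent the patients are randomized in blocks and stratified by gender into two groups", without placing this step relative to debond. For Group A it adds: "Two weeks before debonding an impression of the mandibular jaw is taken in order to manufacture the CTC retainer".

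**The concern.** Three points in the model description matter for the treatment comparison.

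- **Role of T1.** T1 is taken before the retainer can act. The plan appears to use it as one more response. Using it as a covariate extracts at least as much information in large samples, and the sample is fixed at 104.
- **Status of group-by-time.** It is listed among terms to be tested, and no sentence fixes it in the model. With T1 among the responses, the interaction carries the treatment effect. The group main effect in a model without it averages in a visit at which no retainer effect can exist.
- **Scope of the cast predictors.** The first item in the list covers every digital measurement and sets no limit on visit. It may mean T1 values. Read literally, it also admits follow-up values of other outcomes. These are measured after randomisation and may themselves be affected by the retainer, so adjusting for them could bias the comparison.

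**Working it through.** The plan gives no power, SD or correlation figure to reproduce. The only inputs from the documents are 52 patients per group, the visits T1 to T4 and the significance level of 0.05 (taken as two-sided). Everything else below is an assumption, shown over a range.

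**1. Precision at one follow-up visit.** Let r be the correlation between T1 and follow-up, and k = SD(T1)/SD(follow-up). In units of the follow-up variance:

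- change from T1: V = 1 + k² − 2kr
- T1 as covariate, with its own slope at that visit: V = 1 − r²
- difference: (1 + k² − 2kr) − (1 − r²) = (k − r)², which is never negative and is zero when k = r

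| Adjusted/change variance ratio | r = 0.3 | 0.5 | 0.7 | 0.9 |
|---|---|---|---|---|
| k = 1 | 0.91/1.40 = 0.65 | 0.75/1.00 = 0.75 | 0.51/0.60 = 0.85 | 0.19/0.20 = 0.95 |
| k = 0.7 | 0.91/1.07 = 0.85 | 0.75/0.79 = 0.95 | 0.51/0.51 = 1.00 | 0.19/0.23 = 0.83 |
| k = 0.5 | 0.91/0.95 = 0.96 | 0.75/0.75 = 1.00 | 0.51/0.55 = 0.93 | 0.19/0.35 = 0.54 |

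**2. The same as interval width.** The 95% CI half-width is 1.96 × √(V × 2/52), in follow-up SD units. For k = 1 and no dropout:

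| Half-width | r = 0.3 | 0.5 | 0.7 | 0.9 |
|---|---|---|---|---|
| Change | 0.45 | 0.38 | 0.30 | 0.17 |
| Adjusted | 0.37 | 0.33 | 0.27 | 0.17 |

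**3. Why a slope per visit.** Suppose k = 1 and T1 correlates 0.9/0.7/0.3 with T2/T3/T4. A single slope equal to the average is (0.9 + 0.7 + 0.3)/3 = 0.633, and V = 1 + 0.633² − 2 × 0.633 × r = 0.261/0.514/1.021. Against the change variances 0.2/0.6/1.4 the ratios are 1.31/0.86/0.73, so a common slope would do worse than change at T2. Separate slopes give 0.95/0.85/0.65.

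**4. What would follow if the interaction were removed.** The plan does not state this step. Suppose T1 is a response, the true difference is 0 at T1 and constant afterwards, and the working correlation is AR(1) with parameter rho by visit order. The group main effect then weights T1 by 1/(3 − rho) with three visits and by 1/(4 − 2·rho) with four. A constant 0.50 mm effect is estimated as 0.50 × (1 − weight):

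| rho | Three visits: T1 weight, estimate | Four visits: T1 weight, estimate |
|---|---|---|
| 0 | 33%, 0.33 mm | 25%, 0.38 mm |
| 0.5 | 40%, 0.30 mm | 33%, 0.33 mm |
| 0.8 | 45%, 0.27 mm | 42%, 0.29 mm |

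The probability that a three-visit, 2-df interaction test is non-significant with 52 per group (noncentral chi-square, rho 0.5/0.8) is 35%/4% for an effect of 0.5 SD, 73%/42% for 0.3 SD and 86%/71% for 0.2 SD.

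**5. Price of the adjustment.** If known allocation had shifted T1 by d, the adjusted and change contrasts would differ by d × |1 − r/k|. With d = 0.2 follow-up SD and r = 0.3/0.5/0.7/0.9, this is 0.14/0.10/0.06/0.02 SD for k = 1 and 0.08/0.00/0.08/0.16 SD for k = 0.5.

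**The case against.** The strongest defence is that the plan, read sensibly, is already sound. It speaks of the group effect over time and of changes from T1, and group-by-time is the only interaction listed. The aims give 6 months, 18 months and 5 years. Together these point to a difference in change at each visit, which is an unbiased contrast. This stands. The missing formal contrast is therefore mostly a matter of detail.

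A reader might infer that the plan will dilute the treatment effect. The documents do not support that. Dilution needs T1 as a response, removal of the interaction and reporting of the group main effect. The first is only the natural reading, and the other two are not stated. At 0.5 SD and rho 0.8, the test that might prompt removal would be non-significant in only about 4% of trials.

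It can also be said that the precision gain may be trivial. T1 is the end of active treatment, so its spread may be small for some outcomes. At k = 0.5 and r between 0.3 and 0.7, the variance falls by at most 7% (ratio 0.93). This also stands, and the documents do not show which outcomes would gain.

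What the defence does not answer is the unrestricted scope of the cast predictors, or why the model that is never less precise in large samples should not be used when it costs only wording.

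**Conclusion.** The point holds as a low-cost improvement, not as an error in the plan. With the interaction kept, the planned contrast is valid, and the loss is in precision alone. Under the assumed values, adjustment cuts the variance by anything from nothing (k = r) to 46% (k = 0.5, r = 0.9). With equal SDs the cut is 35% at r = 0.3 and 5% at r = 0.9. These are large-sample figures without dropout.

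The shrinkage of 0.50 mm to between 0.27 and 0.38 mm depends on a removal step that the plan neither states nor excludes. It is a reason to rule the step out, not a prediction. The risk from follow-up values of other outcomes likewise depends on a literal reading, and one clause removes it.

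It would also go too far to infer that T1 was affected by allocation. The Group A impression two weeks before debond suggests that allocation may be known by then, but the documents do not settle the timing and do not say that it influenced finishing.

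**What to change.** In the Statistical analysis section, state for each cast outcome:

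- The responses are T2, T3 and T4 (T2 and T3 for project 1).
- The model contains the T1 value of the same outcome with a slope that may differ by visit, sex (the stratification factor), group, categorical visit and group-by-visit. All are fixed in advance and kept whatever their p-values.
- Any other cast measurement used as a predictor is limited to its T1 value.
- The treatment effect is the adjusted group difference with 95% CI at 6, 18 and 60 months.
- The timing of randomisation relative to debond is given, and the change-from-T1 contrast is reported as a sensitivity analysis.

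The cost is a few sentences. T1 casts are already planned for both groups, so no visit or measurement is added. The model spends up to three T1 slopes and assumes that known allocation did not affect T1; the sensitivity analysis shows how much the result depends on that assumption. The change does not single out one outcome or visit: six outcomes at three visits still make 6 × 3 = 18 contrasts.
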